6.2.6 Management of skin toxicity

For patients with grade 1 toxicity, no specific supportive care is usually needed or indicated. Rash must be reported as an AE. Patients with grade 2 or higher toxicity may be treated with the following suggested supportive measures at the discretion of the investigator: oral minocycline, topical tetracycline, topical clindamycin, topical silver sulfadiazine, diphenhydramine, oral prednisolone (short course), topical corticosteroids, or pimecrolimus.

6.3 Dose Modifications/Delays

6.3.1 General dose modification/Delays

Dose modifications for toxicities not otherwise covered in section 6.2 are listed in the table below. Patients who do not recover to grade 2 or less toxicity within 28 days will be removed from protocol therapy except where noted (ie. pneumonitis). In addition, patients may hold study intervention (pazopanib and everolimus) for greater than 28 days if the patient's physician and the overall principal investigator, [name], agree that the patient is deriving clinical benefit from the study drugs. Dose modifications for specific toxicities are covered in sections 6.2 and 6.3.

All toxicities, both during the DLT period and after it has been completed, will follow the guidelines laid out here in sections 6.2 and 6.3.

For definition of a Dose Limiting Toxicity, refer back to section 5.4.

Non-hematological toxicity

Toxicity	Actions
Non-Infectious Pneumonitis	Please refer to section 6.2.3
Reactivation of HBV or HCV flare	Please refer to section 6.2.4
Non-hematological toxicity Grade 2 (except pneumonitis – refer to section 6.2.3) (except hypertension, proteinuria, venous or arterial thrombosis, QTc prolongation- refer to section 6.3.2) (except hepatotoxicity – refer to section 6.3.3) (except elevated amylase and lipase- refer to section 6.3.5)	If the toxicity is tolerable to the patient, maintain the same dose. If the toxicity is “intolerable” to patient, interrupt pazopanib and everolimus until recovery to grade ≤ 1 . Then reintroduce pazopanib and everolimus at same dose. If event returns to “intolerable” grade 2, then interrupt pazopanib and everolimus until recovery to grade ≤ 1 . Then reintroduce pazopanib and everolimus at one dose level lower. If event is recurrent “intolerable” grade 2 despite two dose reductions, discontinue pazopanib and everolimus.
Grade 3 or 4 (except hyperlipidemia ¹) (except pneumonitis – refer to section 6.2.3) (except hypertension, proteinuria, venous or arterial thrombosis, QTc prolongation- refer to section 6.3.2) (except hepatotoxicity – refer to section 6.3.3)	Interrupt pazopanib and everolimus until recovery to grade ≤ 1 . Then reintroduce pazopanib and everolimus at one dose level lower. No more than 2 dose reductions allowed.
Stomatitis / oral mucositis / mouth ulcers	See section 6.2.3 Management of stomatitis / oral mucositis / mouth ulcers
Recurrence of grade 3 toxicity after dose reduction	Reduce dose to the next lower dose level, if available. The lowest possible dose level of everolimus is 5 mg every other day (2.5 mg daily). Below this level, everolimus must be discontinued.
	Interrupt everolimus administration until resolution to \leq grade 1 or baseline

Intolerable grade 2 mucositis, or grade 3 AE, except hyperglycemia or hypertriglyceridemia or hypercholesterolemia (see Section 6.2.2.)	
grade / value.
 
If resolution occurs within \leq 7 days, everolimus should be re-started at the dose level prior to interruption.
 
If resolution takes $>$ 7 days, or if event recurs within 28 days, hold everolimus until recovery to \leq grade 1 or baseline grade / value and reintroduce everolimus at one dose level lower, if available.
 
Patients will be withdrawn from the study if they fail to recover to \leq grade 1 or baseline grade / value within 28 days.

Any other grade 4	
Hold everolimus until recovery to grade \leq 1 or baseline value
 
Reintroduce everolimus at one dose level lower, if available.

Grade 3 or 4 clinical liver failure (asterixis or encephalopathy/coma)	
Discontinue everolimus and Pazopanib

Recurrence of intolerable grade 2 mucositis or grade 3 event after dose reduction	
Reduce dose to the next lower dose level, if available. The lowest possible dose level of everolimus is 2.5 mg daily. Below this level, everolimus must be discontinued. If toxicity recurs at Grade 3, consider discontinuation.

Recurrence of grade 4 after dose reduction	
Discontinue everolimus and Pazopanib

Any non-hematologic toxicity requiring everolimus interruption for $>$ 28 days	
Discontinue everolimus and Pazopanib

¹Grade 3 hyperlipidemia (hypercholesterolemia and/or hypertriglyceridemia) should be managed using medical therapies without dose reduction (see Section 6.2.2).

Hematological toxicity

Grade 2 Thrombocytopenia (platelets $<75 - 50 \times 10^9/L$)	
Interrupt pazopanib and everolimus until recovery to grade \leq 1 ($\geq 75 \times 10^9/L$). Then reintroduce pazopanib and everolimus at initial dose. If thrombocytopenia again returns to grade 2, interrupt pazopanib and everolimus until recovery to grade \leq 1. Then reintroduce everolimus at one dose level lower. No more than two dose reductions are allowed.

Grade 3 or 4 Thrombocytopenia (platelets $<50 \times 10^9/L$)	
Interrupt pazopanib and everolimus until recovery to grade \leq 1 ($\geq 75 \times 10^9/L$). Then resume pazopanib and everolimus at one dose level lower. If grade 3 or 4 thrombocytopenia recurs, discontinue pazopanib and everolimus.

Grade 1 & 2 Neutropenia (neutrophils $\geq 1 \times 10^9/L$)	
Grade 3 Neutropenia (neutrophils $<1, \geq 0.5 \times 10^9/L$)	
No modification of dose.

	
Interrupt everolimus and Pazopanib until resolution to grade ≤ 1 or baseline value
 
If AE resolution occurs ≤ 7 days, reintroduce everolimus and pazopanib at the same dose level.
 
If AE resolution occurs > 7 days (within 28 days), reintroduce everolimus and pazopanib at one dose level lower, if available. Discontinue patient from study therapy if recurrent grade 3 or greater neutropenia after two dose reductions.

Grade 4 Neutropenia (neutrophils $< 0.5 \times 10^9/L$)
	
Interrupt pazopanib and everolimus until recovery to grade ≤ 1 (neutrophils $\geq 1.5 \times 10^9/L$). Then resume pazopanib and everolimus at one lower dose level. If grade 3 or grade 4 neutropenia occurs despite two dose reductions, discontinue pazopanib and everolimus.

Grade 3 febrile neutropenia (not life-threatening)
	
Hold further pazopanib and everolimus until the ANC $\geq 1,500/\text{mm}^3$ and fever has resolved and antibiotics are discontinued. Then resume pazopanib and everolimus at one dose level lower. If febrile neutropenia recurs, discontinue pazopanib and everolimus.

Grade 4 febrile neutropenia (life-threatening)
	
Discontinue pazopanib and everolimus.

Any hematological or non-hematological toxicity requiring interruption for ≥ 4 weeks
	
Discontinue pazopanib and everolimus

6.3.2 Management of hypertension, proteinuria, hemorrhage/bleeding, venous and arterial thrombosis, QTc prolongation

AE Terms & Descriptions	Dose Modification Algorithms

Hypertension
	

(A). Asymptomatic and persistent SBP of ≥ 140 and < 170 mmHg, or DBP ≥ 90 and < 110 mmHg, or a clinically significant increase in DBP of ≥ 20 mmHg.
	
Step 1. Pazopanib and everolimus at the current dose.
 
Step 2. Adjust current or initiate new antihypertensive medication(s).
 
Step 3. Titrate antihypertensive medication(s) during next 2 weeks as indicated to achieve well-controlled^a blood pressure (BP). If BP is not well-controlled within 2 weeks, consider referral to a specialist and go to scenario (B).

AE Terms & Descriptions	Dose Modification Algorithms
(B). Asymptomatic SBP \geq 170 mmHg, or DBP \geq 110 mmHg, or failure to achieve well-controlled BP within 2 weeks in scenario (A).	Step 1. Interrupt pazopanib and everolimus. Step 2. Adjust current or initiate new antihypertensive medication(s). Step 3. Titrate antihypertensive medication(s) during next 2 weeks as indicated to achieve well-controlled BP. ^a Step 4. Once BP is well-controlled, dose reduce pazopanib and everolimus and restart at one dose level lower.
(C). Symptomatic hypertension or recurring SBP \geq 170 mmHg, or DBP \geq 110 mmHg, despite modification of antihypertensive medication(s)	Step 1. Interrupt pazopanib and everolimus Step 2. Adjust current or initiate new antihypertensive medication(s). Step 3. Titrate antihypertensive medication(s) during next 2 weeks as indicated to achieve well-controlled BP ^a . Referral to a specialist for further evaluation and follow-up is also recommended. Step 4. Once BP is well-controlled, dose reduce pazopanib and everolimus and restart at one dose level lower.
(D). Refractory hypertension unresponsive to above interventions.	Discontinue pazopanib and everolimus and continue follow-up per protocol.
a. Well-controlled BP defined as mean SBP $<$ 140 mmHg and mean DBP $<$ 90 mmHg.	

Proteinuria

24-hr urine protein \geq 3 grams	Step 1. Interrupt pazopanib and everolimus. Step 2. The 24-hour urine protein will be tested weekly until the level is $<$ 3 grams. Then, restart pazopanib and everolimus dose reduced one dose level. Step 3. If 24-hour urine protein \geq 3 grams recurs once, repeat Steps 1 and 2. Step 4. If 24-hour urine protein \geq 3 grams recurs after 2 dose reductions, discontinue pazopanib and everolimus
------------------------------------	--

Hemorrhage /Bleeding

Grade 1	Continue pazopanib and everolimus with current dose; monitor as clinically indicated.
Grade 2	Step 1. If pulmonary or GI bleed (other than hemorrhoidal bleeding), discontinue pazopanib and everolimus and continue follow-up per protocol. Otherwise, interrupt pazopanib and everolimus until the AE resolved to \leq Grade 1. Step 2. Restart pazopanib and everolimus; reduce dose by one dose level and consult with study PI, monitor as clinically indicated.
Grade 3 or 4, or Recurrent \geq Grade 2 event after	Discontinue pazopanib and everolimus and continue with follow-up per protocol.

AE Terms & Descriptions	Dose Modification Algorithms
dose interruption/reduction.	
Venous Thrombosis (DVT, PE)	
Grade 2	Continue everolimus and pazopanib at the same dose
Grade 3	
Step 1. Interrupt pazopanib and everolimus.
 
Step 2. Initiate and monitor anticoagulation as clinically indicated.
 
Step 3. Resume pazopanib and everolimus with one dose reduction only if all of the following criteria are met:
 
 • The subject must have been treated with anticoagulant at the desired level of anticoagulation for at least one week. • No Grade 3 or 4 or clinically significant Grade 2, hemorrhagic events have occurred while on anticoagulation treatment. 
Subject should be monitored as clinically indicated during anticoagulation treatment and after resuming study treatment. When treating with warfarin, international normalized ratio (INR) should be monitored within three to five days after any change in pazopanib and everolimus dosing (eg, re-initiating, escalating/de-escalating, or discontinuing pazopanib and everolimus), and then at least weekly until the INR is stable. The dose of warfarin (or its derivatives) may need to be adjusted to maintain the desired level of anticoagulation

Grade 4 and/or PE	Discontinue pazopanib and everolimus and continue follow-up per protocol.
Arterial Thrombosis/Ischemia	
Any Grade	Discontinue pazopanib and everolimus and continue follow-up per protocol.
Prolongation of QTc Interval: If the QTc is prolonged, the ECG should be manually read to ensure accuracy of the reading. The values below refer to manually-read ECGs.	
QTc \geq 480 < 500 msec	Continue pazopanib and everolimus; monitor as clinically indicated.
QTc \geq 500 msec	Discontinue pazopanib and everolimus and continue follow-up per protocol.

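### Sections 6.3.1 and 6.3.2 give different instructions for the same bleed: hemorrhage is missing from the 6.3.1 exceptions and no sentence says which section takes precedence

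*Combined protocol and SAP*

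**What the plan says.** Section 6.3.1 opens by limiting its table to toxicities that section 6.2 does not already cover. The same paragraph then says that specific toxicities are dealt with in 6.2 and 6.3.

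The grade 2 row and the grade 3 or 4 row of the non-hematological table both carry this exception: "except hypertension, proteinuria, venous or arterial thrombosis, QTc prolongation- refer to section 6.3.2". The section they point to is headed "6.3.2 Management of hypertension, proteinuria, hemorrhage/bleeding, venous and arterial thrombosis, QTc prolongation", and it contains a graded hemorrhage/bleeding block.

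Instructions in the general table (6.3.1):
- Grade 2: "If the toxicity is tolerable to the patient, maintain the same dose". If the event is intolerable, both drugs are interrupted until grade 1 or less and reintroduced at the same dose.
- Grade 3 or 4: both drugs are interrupted until grade 1 or less. "Then reintroduce pazopanib and everolimus at one dose level lower. No more than 2 dose reductions allowed".

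Instructions in the bleeding block (6.3.2):
- Grade 2: "If pulmonary or GI bleed (other than hemorrhoidal bleeding), discontinue pazopanib and everolimus and continue follow-up per protocol". For any other grade 2 bleed, both drugs are interrupted until grade 1 or less, and then: "Restart pazopanib and everolimus; reduce dose by one dose level and consult with study PI, monitor as clinically indicated".
- Grade 3 or 4, or a recurrent bleed of grade 2 or higher after interruption or reduction: "Discontinue pazopanib and everolimus and continue with follow-up per protocol".

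**The concern.** Someone who looks up a bleed in 6.3.1 finds a complete instruction and nothing that sends them on to 6.3.2. Someone who opens 6.3.2 finds a different instruction. For a severe bleed, one ends in re-exposure at a lower dose and the other in stopping both drugs.

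The protocol itself treats bleeding as important. Section 6.1.1 says that hemorrhage on everolimus can be fatal if severe drug-related thrombocytopenia develops. Section 2.3 reports thrombocytopenia in 56% of the phase I patients on this combination, one of them at grade 3. Section 3.3.7 allows patients on therapeutic warfarin to enroll.

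Two centers take part in the expansion phase (section 12.2). Each could handle the same event differently and be following the protocol. Treatment exposure and the recorded reason for coming off treatment (section 5.8) would then depend on which table was opened.

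**Working it through.** No calculation underlies the claim, so the check is a comparison of text.

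**Step 1. Topics.** Counting venous and arterial thrombosis as one, the 6.3.2 heading has five topics: hypertension, proteinuria, hemorrhage/bleeding, thrombosis and QTc prolongation. Four of the five are in the 6.3.1 exception lists. Hemorrhage/bleeding is in neither row.

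**Step 2. Does a bleed fall under the general rows?** The opening sentence of 6.3.1 removes only what 6.2 covers, and 6.2 has no bleeding subsection. The hematological table deals with thrombocytopenia, neutropenia and febrile neutropenia, plus a row on long interruptions. Read literally, a bleed stays under the non-hematological rows.

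**Step 3. Actions side by side.**

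| Event | 6.3.1 | 6.3.2 |
|---|---|---|
| Grade 2 pulmonary or GI bleed, not hemorrhoidal | Same dose if tolerable; if not, interrupt and restart at the same dose | Discontinue both |
| Other grade 2 bleed | As above | Interrupt, restart one level lower |
| Grade 3 or 4 bleed | Interrupt, restart both one level lower | Discontinue both |
| Grade 3 recurring after a reduction | Reduce again, if a lower level exists | Discontinue both |

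The two sections differ in every line.

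**Step 4. Other general rows in 6.3.1.** The table continues with a row for intolerable grade 2 mucositis or any grade 3 event, excepting only hyperglycemia and lipid events. It holds everolimus and restarts it at the prior dose if the event resolves within 7 days. If resolution takes longer, or the event recurs within 28 days, the instruction is to "reintroduce everolimus at one dose level lower, if available". A further row, for any other grade 4 event, holds everolimus and restarts it one level lower. Both can be read to reach a bleed, and neither matches 6.3.2.

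**Step 5. Is precedence stated?** The sentence sending specific toxicities to 6.2 and 6.3 does not rank the tables, because 6.3 contains both. Elsewhere the protocol does state precedence: a footnote in 6.3.3 puts the hepatitis C flare guidance first. There is no such statement for bleeding.

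**Step 6. How often might it arise?** Sections 2.1.2.1 and 6.1.2 give serious hemorrhage as 1.4% in pazopanib trials, on a denominator of 1000. Section 14.1 gives 26 eligible treated patients and 29 enrolled. Assuming that rate applies here and patients are independent, the chance of at least one event is 1 − (1 − 0.014)^n:
- n = 26: 1 − 0.986^26 = 1 − 0.693 = 0.307
- n = 29: 1 − 0.986^29 = 1 − 0.664 = 0.336

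**The case against.** The strongest reply is that the specific rule overrides the general one. Section 6.3.1 is titled as general, its lead-in points to specific guidance, and 6.3.2 names bleeding in its heading and grades it. On that view this is a missing cross-reference, not two rules of equal standing. The reading is plausible and many investigators would adopt it. It remains an inference, and the authors did not rely on it for the other four topics, which they excepted by name in both rows.

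Second, the exception lists are visibly unreliable. Amylase and lipase are excepted at grade 2 but not at grade 3 or 4, although 6.3.4 covers all three grades. The reference given for them is 6.3.5, and stomatitis is sent to 6.2.3 instead of 6.2.1. This stands. A reader might infer from the omission that the authors meant bleeding to stay under the general restart rule. The documents do not support that; a drafting slip explains it equally well.

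Third, the rows in Step 4 are weaker evidence. The grade 3 row overlaps hypertension and thrombosis as much as bleeding, and it conflicts with the grade 3 or 4 row of its own table. The grade 4 row says other, which may exclude events that have their own rule. Both are a general overlap in the table, to be cleared up in the same edit.

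Fourth, exposure to the problem may be small. Section 6.1.1 calls serious drug-related hemorrhage on everolimus exceptional. Sections 3.4.10, 3.4.12 and 3.4.14 exclude active bleeding, recent hemoptysis and GI conditions that raise bleeding risk. The monthly two-center calls in section 12.2 make lasting divergence less likely. All of this bears on frequency and detection. None of it removes the contradiction.

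**Conclusion.** The concern holds as an internal inconsistency. For bleeds of grade 2 and above, 6.3.1 and 6.3.2 prescribe different actions, and the text does not say which applies. This follows from the wording alone and needs no assumption about event rates. It merits correction because the event is safety-critical and the edit is small.

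Three stronger readings go beyond the documents:
- It is not shown that the centers have acted, or will act, differently. The text only permits it.
- The 31% to 34% is not the chance that a patient is managed under the wrong table. It is the chance of at least one serious hemorrhage, if the pazopanib rate carries over to the combination and to this population. Serious is also not the same as grade 3 or 4. The documents give no rate for grade 2 bleeds or for bleeding from urothelial tumors.
- No effect on the primary endpoint, objective response, is demonstrated. The plausible effect is on exposure and off-treatment reasons.

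Nothing here says which clinical action is right.

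**What to change.** Reconcile 6.3.1 and 6.3.2 for hemorrhage/bleeding so that a single stated rule applies at each grade and on recurrence. The edit should cover the grade 2 row, the grade 3 or 4 row, and the later 6.3.1 rows for grade 3 events, recurrent grade 3 events and other grade 4 events. It should also state which section takes precedence where a general and a specific row both apply. The sponsor's clinical team decides which action stands. A cross-reference from one section to the other would itself select a rule, so it should follow that decision.

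Notify both centers when the amendment is approved. The faulty references to 6.3.5 and 6.2.3 can be corrected in the same edit.

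Cost: a table-wording amendment with IRB review and a site memo. No added procedures, visits or patients.

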Nine patients were enrolled in the phase I portion of this study. Two patients on dose level 0 (pazopanib 600 mg daily and everolimus 5 mg daily) experienced dose limiting toxicities (grade 3 rash and pruritus and grade 3 thrombocytopenia requiring a dose reduction). Therefore, three patients were treated at dose level -1 per protocol. None of these three patients experienced a protocol-defined dose-limiting toxicity. Therefore, another three patients were treated at dose level -1 (pazopanib 400 mg daily and everolimus 5 mg daily) without any dose-limiting toxicities. Therefore, per protocol, dose level -1 was defined as the maximum tolerated dose.

Toxicity	Maximum Grade			
	G1	G2	G3	G4
Febrile neutropenia	-	-	1	-
Neutropenia	1	-	-	-
Thrombocytopenia	3	1	1	-

Hematologic toxicities (see table above) included febrile neutropenia (11%), neutropenia (11%), thrombocytopenia (56%), and anemia (36%). Grade 3 febrile neutropenia and thrombocytopenia each occurred in 1 patient. Non-hematologic toxicities were varied, though many were expected based on the known toxicities of everolimus and pazopanib. One patient did experience a grade 3 pneumothorax, which was possibly related to study therapy. Other non-hematologic toxicities included anorexia (11%), bone pain (11%), diarrhea (22%, 11% G3), fatigue (56%), dysgeusia (11%), headache (11%), hypertension (22%), mucositis (33%), musculoskeletal (muscle stiffness after prolonged periods of sitting, 11%), nausea (44%), palmo-plantar erythrodysesthesia syndrome (11%), pneumonia (11% G3), pruritus (11% G3), rash (33%, 11% G3), vomiting (33%), and weight loss (11%). Toxicities noted in laboratory evaluations were generally consistent with what is expected with both agents administered separately. G3 and 4 laboratory toxicities included increased ALT, hypophosphatemia, and hypouricemia each in 1 patient, and increased lipase in 2 patients.

Treatment was generally well tolerated at the MTD. Two of 6 patients came off treatment after 2 cycles because of toxicity. The others stopped treatment due to disease progression or physician decision.

Antitumor activity

Encouraging antitumor activity was noted in the bladder cancer patients treated on pazopanib and everolimus. Of five urothelial cancer patients evaluable, 3 had stable disease for 4 months, 4 months and 5.5 months respectively. One patient had a complete response which lasted 14 months.

Tumor type	(n)	Best objective response

Bladder	5	3 SD, 1CR, 1 NE

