6.3.4 Dose modifications for elevated amylase and lipase

Event	Dose Modification Algorithm

Grade 2 elevation of amylase and lipase without symptoms of pancreatitis
	
Monitor amylase and lipase every other week, continue study therapy at the same dose level

Grade 2 elevation of amylase and lipase with symptoms of pancreatitis	Hold study therapy until both labs and symptoms are grade 1 or less. Consider restarting study therapy with a dose reduction if the patient is known to be deriving clinical benefit
Grade 3 elevation of amylase and lipase without symptoms of pancreatitis	Check amylase and lipase weekly until grade 2 or less, monitor for symptoms weekly (phone contact or visit) until grade 2 or less, and continue study therapy at the same dose level. Consider GI consultation.
Grade 3 elevation of amylase and lipase with symptoms of pancreatitis	Hold study therapy until both laboratory testing and symptoms are grade 1 or less. GI consultation is recommended. Consider restarting study therapy with a dose reduction if the patient is known to be deriving clinical benefit from treatment.
Grade 4 elevation of amylase and lipase without symptoms of pancreatitis	Hold study therapy until grade 2 or less, restart with one dose-level reduction if the patient is known to be deriving clinical benefit from treatment. GI consultation recommended.
Grade 4 elevation of amylase and lipase with symptoms of pancreatitis	Hold study therapy until both laboratory testing and symptoms are grade 1 or less. GI consultation is recommended. Consider restarting study therapy with a dose reduction if the patient is known to be deriving clinical benefit from treatment.

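### For grade 3 amylase/lipase elevation without symptoms, sections 6.3.1 and 6.3.4 give conflicting dose instructions, and no text says which governs

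*Combined protocol and SAP*

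**What the plan says.** Section 6.3.1 opens its table by defining its scope: "Dose modifications for toxicities not otherwise covered in section 6.2 are listed in the table below". In the non-hematological part, the grade 2 row carries a list of exceptions that ends with amylase and lipase: "except elevated amylase and lipase- refer to section 6.3.5".

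The next row begins "Grade 3 or 4 (except hyperlipidemia ¹) (except pneumonitis – refer to section 6.2.3" and goes on to exempt the section 6.3.2 events and hepatotoxicity. It does not mention amylase or lipase. Its action is to stop both drugs until grade 1 or lower, and then: "Then reintroduce pazopanib and everolimus at one dose level lower. No more than 2 dose reductions allowed".

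The enzyme rules are in "6.3.4 Dose modifications for elevated amylase and lipase", the last subsection of section 6. For grade 3 without symptoms of pancreatitis, after weekly enzyme checks, it says: "monitor for symptoms weekly (phone contact or visit) until grade 2 or less, and continue study therapy at the same dose level".

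Two later rows of the 6.3.1 table also catch these events. One covers grade 3 adverse events with only glucose and lipid exceptions, and the other covers any other grade 4 event. Both give instructions for everolimus only.

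Section 6.3.1 also states: "Dose modifications for specific toxicities are covered in sections 6.2 and 6.3".

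**The concern.** An investigator with a grade 3 amylase or lipase result in a patient who feels well finds two instructions that cannot both be followed: continue unchanged, or stop both drugs and come back lower. The row-by-row exceptions are how the table hands a toxicity over to its own section. Amylase/lipase is handed over at grade 2 and not at grade 3 or 4.

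In the expansion cohort, Table 6 allows one dose reduction, and a patient who needs more than one stops study therapy, subject to a discretionary monotherapy option. So the reading chosen decides whether an asymptomatic laboratory value leaves dosing untouched or uses the only reduction available. Sections 5.2.1 and 9.2 have both enzymes tested on day 1 of every cycle, so such results will be found. Section 12.2 describes two research teams in the expansion phase, and they could apply different rules within one small cohort.

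**Working it through.** The plan gives no figure to reproduce here. The check is a comparison of texts, followed by a rough frequency.

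**1. Does the general table apply?** Its stated limit is toxicities covered in 6.2. Section 6.2 deals with stomatitis, lipids and glucose, pneumonitis, hepatitis, infections and skin. Amylase and lipase are not there, so on the wording they fall within the table.

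**2. Which exceptions are repeated?** Pneumonitis, the listed 6.3.2 events and hepatotoxicity appear in both the grade 2 row and the Grade 3 or 4 row. Amylase/lipase is the only grade 2 exception that is not repeated.

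**3. Cell-by-cell comparison.**

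| Event | 6.3.1, Grade 3 or 4 row | 6.3.4 | Result |
|---|---|---|---|
| Grade 3, no symptoms | Stop both drugs to grade ≤1, restart one level lower | Same dose, weekly checks | Opposite |
| Grade 4, no symptoms | As above | Hold to grade ≤2, restart one level lower if the patient is benefiting | Same direction; threshold and restart condition differ |
| Grade 3, symptoms | As above | Hold to grade ≤1, restart at a reduced dose may be considered if benefiting | Broadly compatible; restart discretionary in 6.3.4 |
| Grade 4, symptoms | As above | As for grade 3 with symptoms | Broadly compatible; restart discretionary in 6.3.4 |

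One cell of four is opposite, one differs in threshold and condition, and two are broadly compatible.

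**4. The later rows of 6.3.1.** The grade 3 adverse event row interrupts everolimus and restarts it at the prior dose if the event resolves within 7 days, otherwise one level lower. That is a third answer for grade 3 without symptoms. The row for any other grade 4 event holds everolimus to grade ≤1 or baseline and restarts it one level lower. Neither row exempts amylase/lipase.

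**5. The cross-reference.** The grade 2 row cites 6.3.5. Section 6 ends at 6.3.4 and section 7 follows.

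**6. How often could it matter?** Inputs:
- n = 26 eligible treated patients (section 14.1).
- Grade 3-4 amylase 4% and lipase 9%, from the single-agent pazopanib phase II renal cell trial of 225 patients (section 2.1.2.1).
- Phase I of this trial: "increased lipase in 2 patients" at grade 3 or 4, out of 9 (section 2.3).

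The expected count is n × p, and the chance of at least one case is 1 − (1 − p)^n. The assumption is that the rates carry over.
- Amylase: 26 × 0.04 = 1.04; 1 − 0.96^26 = 0.65.
- Lipase: 26 × 0.09 = 2.34; 1 − 0.91^26 = 0.91.
- With n from 25 to 29, the expected counts are 1.0 to 1.2 and 2.3 to 2.6.
- The overlap between the two enzymes is not given. Either one elevated lies between 9% (full overlap) and 4% + 9% = 13% (none), or 2.3 to 3.4 of 26.
- Phase I: 2/9 = 22%, and 26 × 2/9 = 5.8. The exact 95% interval for 2/9 is about 3% to 60%, which is from under 1 to about 16 of 26, so it is no basis for a projection.

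All these rates pool grade 3 with grade 4 and symptomatic with asymptomatic cases. Each is therefore an upper bound for asymptomatic grade 3.

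**The case against.** The best defence is that the specific section plainly governs. Section 6.3.1 is headed as general and points to 6.2 and 6.3 for specific toxicities. Section 6.3.4 has its own grade 3 and 4 rows split by symptoms, and these would serve no purpose if the general row applied. The exception lists are not complete in any case: hemorrhage has its own rules in 6.3.2 and appears in neither list. The dose-limiting toxicity definition in 5.4.2 also sets asymptomatic, clinically insignificant grade 3 laboratory findings apart.

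This stands as a likely reading and lowers the risk of misapplication. It does not settle the matter. The pointer sentence names 6.3, which contains the general table itself, and it ranks nothing. Where precedence is intended, the protocol says so, as in the 6.3.3 footnote on hepatitis C flare.

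Several stronger conclusions are tempting but unsupported:
- **All grade 3-4 cases face opposite rules.** Only grade 3 without symptoms does.
- **The dead 6.3.5 reference causes the conflict.** It sits in the grade 2 row and is a separate slip. The cause is the exception missing from the Grade 3 or 4 row.
- **About 6 expansion patients would be affected.** That projects 2 of 9 pooled grade 3-4 cases with no symptom status or dose level given. Three of the nine patients received pazopanib 600 mg, not the expansion dose of 400 mg.
- **A second event necessarily ends treatment.** After Table 6, a patient with stable disease or better who cannot tolerate one agent may continue on the other after discussion with the overall principal investigator.
- **The response endpoint is compromised.** Nothing in the documents shows this.

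**Conclusion.** The concern holds in a limited form, and the text is wrong as written. For grade 3 amylase/lipase elevation without symptoms, 6.3.1 and 6.3.4 contradict each other, and a later row of 6.3.1 adds an everolimus-only rule. For grade 4 without symptoms, the discrepancy is secondary: recovery to grade ≤1 against ≤2, and whether restart depends on benefit. The symptomatic cells need only minor alignment.

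Taking each single-agent rate on its own, about 1 to 2 of 26 patients would have a grade 3-4 elevation, and at least one case is more likely than not (0.65 for amylase, 0.91 for lipase). This assumes that rates from a different tumour type under pazopanib alone carry over to this combination. The number with grade 3 and no symptoms cannot be derived from the documents.

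**What to change.** Reconcile the Grade 3 or 4 row of 6.3.1, its later rows for grade 3 adverse events and any other grade 4 event, and section 6.3.4, so that exactly one rule applies to amylase/lipase elevation at each grade and symptom status. Changing only the Grade 3 or 4 row would leave the later rows in conflict. Add a sentence saying which section governs when the general table and a specific section both apply. Correct the grade 2 reference from 6.3.5 to 6.3.4.

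Which rule applies is the sponsor's clinical decision. The cost is a few lines of table wording in an amendment, with no change to sample size, endpoints or analysis.
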